8.6 Patients selection

A paediatric patient in the growth phase, i.e., with open growth plates at the time of treatment, affected by angular deformities and/or femoral and/or tibial length discrepancies who, in the Investigator's sole judgement, had a valid indication for surgical treatment with the 8-Plate Plus and was treated with the investigational device, will be considered eligible for retrospective data collection as defined in the Clinical Investigation Plan.

Eligible patients who meet the following inclusion criteria and none of the exclusion criteria will be deemed suitable for participation in this Clinical Investigation.

8.6.1 Inclusion criteria

A patient will be considered eligible for participation if:

- he/she has been diagnosed with an angular deformity or a femoral and/or tibial length discrepancy;

- at the time of treatment, he/she was younger than 18 years of age;
- at the time of treatment, the growth plates of the treated limb(s) were not yet closed;
- in the opinion of the Investigator, the angular deformity and/or length discrepancy represented a valid indication for surgical treatment with tension band plates;
- the deformity was treated with the 8-Plate Plus, in accordance with the manufacturer's Instructions for Use;
- the treatment with the 8-Plate Plus was completed and the patient underwent at least one follow-up visit after plate removal;
- the clinical data of the patient required for the evaluation of the device's safety and clinical benefit are still available.

8.6.2 Exclusion criteria

A patient will not be considered eligible for participation if:

- he/she was treated with the 8-Plate Plus to correct deformities of the upper limbs only and not of the lower limbs;
- his/her clinical data are no longer accessible and/or do not allow the evaluation of the safety and clinical benefit of the investigational device;
- he/she had a medical condition that constitutes a contraindication to treatment with the 8-Plate Plus according to the manufacturer's Instructions for Use;
- he/she was concomitantly treated with a non-permitted device that could not be removed without compromising the patient's safety.

8.7 Number of Patients Expected to be Enrolled

The sample size was therefore calculated by estimating the number of implants required so that the confidence limits of the study's primary endpoint for the 8-Plate Plus (i.e., the percentage of subjects who experienced at least one complication certainly or possibly related to the investigational device, as described above) fall within the safety profile of the state of the art for this treatment, namely within the safety data reported in the literature for its predecessor (the GGS) and for other equivalent medical devices.

Specifically, the scientific literature reports that the percentage of patients treated with a tension band plate for a lower limb deformity who experienced at least one device-related complication ranges from 3% to 12%, depending on several factors, primarily the heterogeneity of the primary diagnosis [7].

Assuming that the expected percentage of patients with at least one complication certainly or possibly related to the device for the 8-Plate Plus will be 3%, the sample size calculation showed that, in order for the upper limit of the 95% confidence interval for the primary endpoint (calculated using the exact binomial method) to remain below 12% (i.e., 9.94%), 70 implants are required.

As each patient may have been treated for the correction of multiple deformities located in different long bones, it is understood that each eligible subject may contribute data for more than one implant (on average 2). For this reason, approximately 40 patients are expected to be enrolled.

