SAMPLE SIZE CALCULATION	
For the aim of the sample size calculation, the safety profile of GGPSP will be compared to safety data reported in the scientific literature for the treatment of lower limb deformities by the means of guided growth performed by tension band plate. The sample size, therefore, was calculated estimating the required number of subjects so that the primary endpoint of the Study for GGPSP (i.e. percentage of subjects that experienced at least one complication as above described) ranges within the state-of-art safety profile of this treatment, that is, it is within the safety data reported in the literature for its previous version (the GGS) and for equivalent medical devices. Specifically, the scientific literature reports that the percentage of patients treated by a tension band plate for a lower limb deformity that faced at least one complication is between 3% and 12% depending on the many factors, mainly the diversity of the primary diagnosis. Assuming the expected percentage of patients with at least one complication for GGPSP will be 3%, 70 implants was calculated to be the sample size of this study so that the upper limit of the 95% confidence interval for the primary endpoint, based on the exact binomial method, is under 12%. Since each patient may have been treated for the correction of multiple localized deformities in different long bones, it is understood that each eligible subject may contribute to the data collection of multiple implants (average 2). For this reason, approximately 40 patients are expected to be enrolled.

2 Medical Device Information

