8.4 Endpoints

In this Clinical Investigation, the two variables selected as the primary and secondary endpoints, intended to measure the primary and secondary objectives of the Investigation respectively, also correspond to the treatment response measures routinely used in the standard clinical practice of the participating Centre, namely:

- **Primary endpoint (safety measure):**

The safety of the 8-Plate Plus will be assessed by the percentage of subjects who, during the observation period — i.e., from plate implantation to the first follow-up visit after plate removal — experienced at least one complication certainly or potentially related to the investigational device. Such complications are defined as:

- a Serious Adverse Device Effect (SADE), expected or unexpected;
- a hardware failure (e.g., breakage, detachment, or bending of the plate or screws).

- **Secondary endpoint (benefit measure):**

The clinical benefit of treatment with the 8-Plate Plus will be assessed by the percentage of subjects who, during the observation period — i.e., from plate implantation to the first follow-up visit after plate removal — achieved the treatment objective, defined as:

- for hemiepiphysiodesis: partial or complete correction of the angular deformity of the femur and/or tibia towards the standard alignment direction (mMPTA and mL DFA between 85° and 89°);
- for epiphysiodesis: partial or complete correction of femoral and/or tibial length discrepancy in relation to the morphologically normal contralateral limb length.

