8.15 Patients Replacement

Subject to prior notification to the Sponsor, and no later than the study database lock, non-evaluable patients may, at the Investigator's discretion, be replaced with a patient who will be assigned a new and unique identification code.

This procedure is intended solely to increase the likelihood of achieving the planned sample size in terms of evaluable implants. It is understood that the Sponsor will also collect, retain, and analyse the data of patients who were prematurely discontinued and subsequently replaced.

9 Clinical Investigation Monitoring Plan

In order to ensure the proper conduct of the study and the accurate recording of study data, at least the following monitoring visits will be foreseen:

- site initiation visit;
- one monitoring visit during the active conduct phase of the study;
- site close-out visit.

It is understood that, if necessary, the Sponsor reserves the right to perform additional monitoring visits during the active phase of the study.

Prior to each visit, the monitor will contact the Investigator to verify availability and schedule the visit date, and will subsequently send written confirmation specifying the purpose of the visit and any documents to be made available.

At each visit, the monitor shall:

- check the updating of study documentation;
- verify that data collection related to the Clinical Investigation is being conducted appropriately and that data are recorded and reported in compliance with this Clinical Investigation Plan, Good Clinical Practice (GCP), and applicable regulations;
- verify the accuracy of the data entered into the case report form against the source data;
- implement any necessary corrective actions.

Note: Written Monitoring Plan

For this type of Clinical Investigation, which is single-centre, observational, and retrospective, a separate written Monitoring Plan is not foreseen, since all necessary information is already included in the Clinical Investigation Plan.

Note:

The Sponsor intends to monitor all reported data related to the inclusion and exclusion criteria, the study endpoint variables, and all information regarding serious and non-serious adverse events. If deemed appropriate and necessary, other study data may also be subject to monitoring.

10 Documentation

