- revise the Clinical Investigation Plan and any study documentation impacted by the amendments, ensuring that all changes are appropriately tracked;
- in the case of non-substantial amendments, promptly notify in writing the participating Site and the corresponding Ethics Committee for information purposes, providing copies of the revised documents;
- in the case of substantial amendments, suspend the Clinical Investigation until a new favourable opinion has been issued by the relevant Ethics Committee.

15 Adverse events

The foreseeable adverse events related to the use of the 8-Plate Plus, as identified through the risk analysis performed during product design, are described in the section “POSSIBLE ADVERSE EFFECTS” of the device’s Instructions for Use (http://abs.orthofix.it/db/resources/PQ_EPP.pdf).

This Clinical Investigation is a retrospective observational study and, therefore, does not pose additional risks to patients or Investigators.

Definitions:

- An *adverse event (AE)* is any undesirable experience associated with the use of the device in a patient.
- An *adverse event* is defined as a *serious adverse event (SAE)* when, as a consequence of such event, the patient:
 - dies;
 - experiences a life-threatening event;
 - requires prolongation of hospitalisation;
 - requires re-hospitalisation;
 - suffers permanent disability;
 - experiences a congenital anomaly or birth defect.

Expected Serious Adverse Device Effects (SADEs) — i.e., those already reported in the device Instructions for Use — are further classified as **E(SADE)** (*Expected SADE*). Conversely, Serious Adverse Device Effects not previously reported in the device Instructions for Use are further classified as **U(SADE)** (*Unexpected SADE*).

All adverse events and adverse device effects associated with the use of the device that occurred during the entire observation period of the Clinical Investigation will be classified and reported to the Sponsor via the electronic database provided by the Sponsor.

Since this is a retrospective Clinical Investigation, serious adverse events (SAEs), having already followed the reporting procedures of the vigilance system, are not subject to prompt notification upon awareness, as otherwise required by GCP (Section 4.11.1).

16 Statistics

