The safety profile of the 8-Plate Plus, as measured in the present Clinical Investigation, will be compared with the safety data reported in the scientific literature for the treatment of lower limb deformities by guided growth performed with equivalent tension-band plates.

The sample size calculation was performed in order to estimate the confidence intervals for the primary endpoint (safety outcome related to treatment response) of the 8-Plate Plus and to enable a reliable comparison with the data reported in the literature.

Accordingly, the sample size was determined by estimating the number of implants required so that the confidence intervals for the study primary endpoint with the 8-Plate Plus would fall within the established safety profile for this treatment, namely within the range of safety data reported in the literature for its predecessor (the GGS) and for equivalent medical devices.

Specifically, the scientific literature indicates that the proportion of patients treated with a tension-band plate for lower limb deformity who experience at least one device-related complication ranges between 3% and 12%, depending mainly on the heterogeneity of the underlying diagnosis.

Assuming that the expected proportion of patients experiencing at least one complication with the 8-Plate Plus is 3%, the sample size calculation showed that, in order for the upper limit of the 95% confidence interval for the primary endpoint (calculated using the exact binomial method) to remain below 12% (i.e., 9.94%), a total of 70 implants (in approximately 40 patients) are required.

The clinical data collected during the present Clinical Investigation will be analysed using descriptive statistics:

- the primary endpoint will be presented as a percentage value with its corresponding 95% confidence interval;
- the secondary endpoint will be presented as a percentage value with its corresponding 95% confidence interval.

The clinical data obtained from this Clinical Investigation will be used to complete the evaluation of the clinical performance and safety of the 8-Plate Plus, with the objective of confirming that the device can be considered safe and effective as hypothesised during its development, based on the preclinical evaluations conducted for CE marking.

17 Publication of Results

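### The primary endpoint and its 3%–12% benchmark are per patient, but the sample size and its 9.94% upper limit count 70 implants; with about 40 patients the expected result has an upper limit of 13.2%

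*Combined protocol and SAP*

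**What the plan says.** Section 8.4 defines the primary endpoint per patient: "The safety of the 8-Plate Plus will be assessed by the percentage of subjects who" had at least one device-related complication, meaning a serious adverse device effect or a hardware failure. The synopsis defines it the same way. Section 8.7 gives the literature range of 3% to 12%, and the expected 3%, as percentages of patients.

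The sample size is in a different unit. The synopsis says it was "calculated estimating the required number of subjects so that the primary endpoint of the Study" falls within the literature range, then gives the answer as 70 implants. Section 8.7 says that for the exact binomial upper limit "to remain below 12% (i.e., 9.94%), 70 implants are required". Section 16 gives the method as "estimating the number of implants required so that the confidence intervals for the study primary endpoint with the 8-Plate Plus would fall within" (meaning inside the literature range), and concludes that "a total of 70 implants (in approximately 40 patients) are required". Sections 1 and 8.7 expect an average of 2 implants per patient. Section 8.15 allows non-evaluable patients to be replaced to help in "achieving the planned sample size in terms of evaluable implants".

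For the analysis, section 16 plans a percentage with a 95% confidence interval. No section gives a per-implant endpoint, a per-implant benchmark, a within-child correlation or an analysis that allows for clustering.

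**The concern.** A second implant in the same child does not add a subject to a percentage-of-subjects endpoint. If the analysis follows section 8.4, the denominator is about 40, not 70, and the interval is wider than stated.

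The alternative, an exact binomial interval on implants, would not rescue the claim. It would ignore the clustering of implants within children, and it would set a per-implant rate against a per-patient range.

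The 9.94% limit is the only quantitative basis for the study size and for the aim of placing the result within the literature range. Section 16 also says the data are to confirm that the device can be considered safe. An ethics committee or Notified Body reading sections 8.7 and 16 is therefore promised a precision that the defined endpoint would not have at the expected result. Leaving the unit unresolved also leaves the denominator of the main safety result open to choice after the data are seen.

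**Working it through.** **Inputs.** Expected rate 3% of patients; threshold 12%; exact binomial 95% interval; 70 implants; about 40 patients (all section 8.7). Average 2 implants per patient (sections 1 and 8.7), so 70 / 2 = 35 patients is taken as a lower case.

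**Method.** Two-sided Clopper–Pearson limits for x events in n units: lower = Beta quantile 0.025 with parameters (x, n − x + 1); upper = Beta quantile 0.975 with parameters (x + 1, n − x).

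**Step 1: reproduce the plan's figure.** 0.03 × 70 = 2.1, rounded to x = 2. For 2/70 the interval is 0.35%–9.94%, which matches. Other conventions do not: the unrounded 2.1 events give 10.16%, a one-sided 95% limit 8.72%, Wilson 9.83% and Wald 6.76%. So 70 was the binomial denominator, the limit is two-sided, and the units are treated as independent.

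**Step 2: the same calculation per patient.** 0.03 × 40 = 1.2, rounded to x = 1 by the same convention.

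| Patients | Events | Exact 95% CI |
|---|---|---|
| 40 | 0 | 0%–8.81% |
| 40 | 1 | 0.06%–13.16% |
| 40 | 2 | 0.61%–16.92% |
| 35 | 0 | 0%–10.00% |
| 35 | 1 | 0.07%–14.92% |

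Rounding is not the cause: the unrounded 1.2 events in 40 give an upper limit of 13.94%.

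**Step 3: chance that the upper limit is below 12% when the true rate is 3%.**
- 40 patients: zero events needed, 0.97^40 = 29.6%. The other 70.4% of studies have an upper limit of 13.2% or more.
- 35 patients: zero events needed, 0.97^35 = 34.4%.
- 70 independent units: at most 2 events (3/70 already gives 12.02%), P(X ≤ 2) = 64.9%.

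**Step 4: both limits inside 3%–12%.** A search over every event count at n = 35, 40, 70 and 80 finds none with a lower limit of at least 3% and an upper limit of at most 12%.

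**Step 5: would a per-implant analysis help?** Assume exactly 2 implants per child. The documents give no within-child concordance, so ranges are shown.
- A 9.94% per-implant rate corresponds to 9.94% per patient if both implants always fail together, and to 1 − (1 − 0.0994)² = 18.9% if they fail independently.
- Suppose the true per-patient rate is 12%. The naive implant limit is below 12% with at most 3/80 (10.57%; 4/80 gives 12.31%) or at most 2/70. The chance of this is:

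| Pattern within an affected child | 40 patients, 80 implants | 35 patients, 70 implants |
|---|---|---|
| Both implants affected | 3.9% | 6.6% |
| Implants independent (6.19% per implant) | 26.3% | 18.4% |
| Exactly one implant affected | 27.7% | 19.2% |

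**The case against.** The strongest counter-argument concerns weight. Section 16 is descriptive, with no hypothesis test, alpha or pass/fail rule. The study is retrospective and uncontrolled, and no child's treatment depends on the sample size. A per-patient percentage with its interval can be computed and interpreted at any n. The error therefore misstates planned precision and does not corrupt the endpoint. That is right, and there is no type I error claim here. It does not remove the problem, because the upper limit below 12% is the sizing criterion in the synopsis and in sections 8.7 and 16, and it is the only reason given for the number chosen.

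Second, the operational criterion is the upper limit alone. A lower limit below 3% is favourable for a complication rate, so step 4 adds little to the unit error. This is fair. It matters only because sections 8.7 and 16 speak of the confidence limits or intervals lying within the literature range, which cannot happen at these sizes.

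Third, the per-implant figures depend on an assumed pattern within children and examine an analysis that the plan does not define. This also stands. They show only that switching to implants is not a safe way out.

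Fourth, a one-sided 95% limit for 1/40 is 11.3%, below 12%. But a one-sided limit for 2/70 is 8.72%, so that is not what the plan calculated.

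**Conclusion.** The concern holds. The endpoint, benchmark and assumed rate are per patient, while the calculation uses implants as independent binomial units. At the expected result the upper limit is 13.2% with 40 patients (14.9% with 35), not 9.94% and not below 12%. The chance of an upper limit below 12% at a true 3% rate is about 30%, against 65% for 70 independent units.

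These figures rest on the plan's own rate, method and rounding convention and on its approximate patient count. Only the per-implant ranges need an outside assumption (2 implants per child, concordance unknown). The correction should be made before the results are analysed.

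**What to change.** 1. In the synopsis and sections 8.7 and 16, state that the patient is the unit of the primary analysis. Replace the 9.94% and the 70-implant requirement with: *With about 40 patients and an expected rate of 3% (about 1 patient with a complication), the exact two-sided 95% CI would be 0.06%–13.2%. The upper limit would be below 12% only with 0 events (8.8%; probability about 30% at a true 3% rate).*
2. In the same sections, reword the aim: *The study estimates the per-patient rate with its 95% CI and describes it against the literature range; it is not sized to place the interval inside that range.* If about 40 patients reflects the records available, say so, because the precision argument no longer supports that number.
3. In section 8.15, express the target in evaluable patients.
4. Report any per-implant rate as descriptive only, define what counts as one implant, use an interval that allows for clustering by patient, and do not compare it with the per-patient 3%–12% range.

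Option, only if the site has enough eligible records (the documents do not say): size in patients. The chance of meeting the limit does not rise steadily with n, so any choice should be stated with its probability.

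| Patients | Most events with upper limit < 12% | Upper limit | Probability at a true 3% rate |
|---|---|---|---|
| 45 | 1 | 11.8% | 61% |
| 58 | 2 | 11.9% | 75% |
| 70 | 2 | 9.94% | 65% |
| 71 | 3 | 11.9% | 84% |

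From 50 to 57 patients, 2 events exceed 12% (13.7% at 50, 12.1% at 57).

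**Cost.** Wording in four places, and no extra patients unless the option is taken. The stated precision becomes less favourable. The plan needs an amendment, and if it is classed as substantial, section 14 applies: "in the case of substantial amendments, suspend the Clinical Investigation until a new favourable opinion has been issued".

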8.8 Enrollment Point

Each eligible patient, for whom the Investigator has verified compliance with the inclusion criteria, will be considered enrolled in the Clinical Investigation at the moment the Investigator assigns the subject a unique, predefined, and sequential study code, according to the data collection procedures described in this Clinical Investigation Plan.

8.9 Clinical Investigation Duration

Given the retrospective nature of the Clinical Investigation and considering that the consent of eligible patients had already been obtained a priori, no study-specific procedures will be required of the patient. The duration of the study therefore foresees 2 months for patient screening and 4 months for retrospective data collection.

It is understood that the Sponsor, after database lock, unless otherwise agreed with the Investigators and/or the Ethics Committees, reserves a period of 4 months for end-of-study activities, namely:

- database review;
- opening and resolution of potential queries to the Investigators;
- drafting of the statistical report;
- drafting of the clinical report;
- site close-out visits;
- end-of-study notifications to the relevant Ethics Committees and Competent Authority.

